Secondary Endpoints	
 • Serious angiographic complications defined as flow-limiting dissection (\geq grade D), perforation, distal embolization, or acute vessel closure as assessed by the angiographic core lab. • IVL Technical Success (post-dil) defined as post-dilatation residual stenosis \leq50% without flow-limiting dissection (\geq Grade D) of the target lesion by angiographic core lab (measured immediately following mandatory post-dilatation). • IVL Device Success defined as the ability to deliver, advance across the target lesion, pressurize, pulse, flush and retrieve the JAVELIN IVL Catheter. • Technical success (final) defined as final residual stenosis \leq30% without flow-limiting dissection (\geq Grade D) of the target lesion by angiographic core lab. • MAE at 6 and 12 months (as a composite and individual components) • Primary Patency at 12 months defined as: 
 ○ Above the knee lesions: freedom from \geq50% restenosis as determined by Duplex Ultrasound (DUS) and freedom from Clinically-Driven Target Lesion Revascularization (CD-TLR) ○ Below the knee lesions: freedom from both total occlusion (100% diameter stenosis by DUS) in all of the target lesions in a flow pathway, as well as a CD-TLR
Study Inclusion Criteria	
Subjects are required to meet all of the following inclusion criteria in order to be enrolled in the study. For lesion characteristics, each target lesion must meet eligibility. A maximum of two (2) target lesions may be treated per subject; target lesions may be in the same limb or in different limbs.
 
General Inclusion Criteria
 
 1. Age of subject is \geq 18 years. 2. Subject is able and willing to comply with all assessments in the study. 3. Subject or subject's legal representative has been informed of the nature of the study, agrees to participate, and has signed the approved consent form. 4. Estimated life expectancy $>$ 1 year. 5. Rutherford Clinical Category 2, 3, 4 or 5 of the target limb(s).

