5.1 Safety Endpoints

The safety endpoints for this study include:

- **PRIMARY: Major Adverse Events (MAE)** at 30 days defined as a composite of:
 - Cardiovascular death
 - Clinically-driven target lesion revascularization (CD-TLR)
 - Unplanned target limb major amputation (above the ankle)
- **MAE** at 6 and 12 months (as a composite and individual components)
- **Serious angiographic complications** defined as flow-limiting dissection (\geq grade D), perforation, distal embolization, or acute vessel closure as assessed by the angiographic core lab.

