7.2.2 Exclusion Criteria

Subjects who meet any of the following exclusion criteria may not be enrolled in the study:

General Exclusion Criteria

1. Rutherford Clinical Category 0, 1 and 6 (target limb).
2. History of endovascular or surgical procedure on the target limb within the last 30 days, or planned within 30 days of the index procedure, with the exception of toe amputation. Note: inflow treatment of non-target lesions is allowed providing successful treatment.
3. Subject in whom antiplatelet or anticoagulant therapy is contraindicated.
4. Subject has known allergy to contrast agents or medications used to perform endovascular intervention that cannot be adequately pre-treated.
5. Subject has known allergy to urethane, nylon, or silicone.
6. Myocardial infarction within 60 days prior to enrollment.
7. History of stroke within 60 days prior to enrollment.
8. Subject has acute or chronic renal disease with eGFR < 30 ml/min/1.73 m² (using CKD-EPI formula), unless on renal replacement therapy.
9. Subject is pregnant or nursing.
10. Subject is participating in another research study involving an investigational agent (pharmaceutical, biologic, or medical device) that has not reached the primary endpoint.
11. Subject has other medical, social or psychological problems that, in the opinion of the investigator, preclude them from receiving this treatment, and the procedures and evaluations pre- and post-treatment.
12. Covid-19 diagnosis within 30 days.

 SHOCKWAVE <small>MEDICAL INC</small>	No.: CP 67398	REV. C
	TITLE: FORWARD PAD IDE Study Protocol	
	CLASS: CLINICAL PROTOCOL	PAGE 22 OF 65

13. Planned use of cutting/scoring balloons, re-entry or atherectomy devices in target lesion(s) during the index procedure.
14. Planned major amputation of target limb.
15. Acute limb ischemia.
16. Occlusion of all the inframalleolar outflow arteries/vessels (i.e., desert foot).
17. Subject already enrolled into this study.

Angiographic Exclusion Criteria

18. Failure to successfully treat clinically significant inflow lesions in the ipsilateral iliac, femoral, or popliteal arteries, defined as ≤30% residual stenosis with no serious angiographic complications (e.g. embolism).
19. Failure to successfully treat significant non-target infrapopliteal lesions, if treated prior to treatment of target lesion(s). Successful treatment is defined as obtaining ≤50% residual stenosis with no serious angiographic complications (e.g., embolism).

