15.0 DEFINITIONS and ABBREVIATIONS

15.1 Study Definitions

Abrupt or Acute Closure: Angiographic documentation of significantly reduced flow due to mechanical dissection, thrombus, or severe vessel spasm in the treatment area.

Acute Limb Ischemia: A sudden decrease in limb perfusion that causes a potential threat to limb viability (manifested by ischemic rest pain, ischemic ulcers, and/or gangrene) in patients who present within two weeks of the acute event.

Adverse Device Effect (ADE): Adverse event related to the use of an investigational medical device.

Note: This definition includes adverse events resulting from insufficient or inadequate instructions for use, deployment, implantation, installation, or operation, or any malfunction of the investigational medical device.

Note: This definition includes any event resulting from use error or from intentional misuse of the investigational medical device.

Note: This includes “comparator” if the comparator is a medical device.

Adverse Event (AE): Untoward medical occurrence, unintended disease or injury, or untoward clinical signs (including abnormal laboratory findings) in subjects, users or other persons, whether or not related to the investigational medical device and whether anticipated or unanticipated.

Note: This definition includes events related to the investigational medical device or the comparator.

Note: This definition includes events related to the procedures involved.

Note: For users or other persons, this definition is restricted to events related to the use of investigational medical devices or comparators.

Amputation (major): Any requirement for amputation above the ankle.

Amputation (minor): Any requirement for amputation below the ankle.

Amputation, Unplanned: An amputation associated with the target limb that occurs between the index procedure and 30 days that was not previously planned as part of the overall treatment strategy.

Ankle-Brachial Index (ABI): The ratio of systolic blood pressure measured at the ankle to systolic blood pressure measured at the brachial artery.

Calcification Classification (PARC): Calcification will be assessed by the angiographic core lab according to the Peripheral Academic Research Consortium (PARC) definition [22].

PARC Degree of Lesion Calcification

Focal	Degree of lesion calcification
Mild	<180° and greater than one-half of the total lesion length

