Limb Ischemia: Deficient supply of oxygenated blood to the tissues in the limbs that is due to obstruction of the inflow of arterial blood characterized by pain and/or discoloration of the limb.

Lithotripsy: A medical procedure for disrupting calculus in the body.

 SHOCKWAVE <small>MEDICAL INC</small>	No.: CP 67398	REV. C
	TITLE: FORWARD PAD IDE Study Protocol	
	CLASS: CLINICAL PROTOCOL	PAGE 57 OF 65

Luminal Patency: Post-procedure residual stenosis <50% as determined by investigator visual assessment or quantitative analysis of the end of procedure angiogram.

Major Adverse Event (MAE): For the purposes of this study, the definition of Major Adverse Event(s) includes:

- cardiovascular death
- target lesion revascularization
- Unplanned target limb major amputation (above the ankle)

Perforation: Puncture of an arterial wall.

Restenosis: Reoccurrence of narrowing or blockage of target lesion.

Rutherford Classification of Critical Limb Ischemia: Clinical staging system for describing PAD. It includes 7 categories:

Grade	Category	Clinical Description
0	0	Asymptomatic
I	1	Mild claudication
	2	Moderate claudication
	3	Severe claudication
II	4	Ischemic rest pain
	5	Ischemic ulceration not exceeding ulcer of the digits of the foot
IV	6	Severe ischemic ulcers or frank gangrene

(ACC/AHA/SCAI/SIR/SVM 2018 Appropriate Use Criteria for Peripheral Artery Intervention – Bailey et al. 2019)

Serious Adverse Device Effect (SADE): Adverse device effect that has resulted in any of the consequences characteristic of a serious adverse even.

Serious Adverse Event (SAE): Adverse event that led to any of the following:

 SHOCKWAVE <small>MEDICAL INC</small>	No.: CP 67398	REV. C
	TITLE: FORWARD PAD IDE Study Protocol	
	CLASS: CLINICAL PROTOCOL	PAGE 58 OF 65

- death,
- serious deterioration in the health of the subject, user, or other persons as defined by one or more of the following:
 - a life-threatening illness or injury, or
 - a permanent impairment of a body structure or a body function including chronic diseases, or
 - in-patient or prolonged hospitalization, or
 - medical or surgical intervention to prevent life-threatening illness or injury, or permanent impairment to body structure or a body function,
 - fetal distress, fetal death, a congenital abnormality, or birth defect including physical or mental impairment.

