10.3. Glossary of Terms and Abbreviations

The Clinical Protocols provide a current Glossary of Terms and Abbreviations.

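### The glossary limits 'unplanned' amputation to the first 30 days, which contradicts the secondary 6- and 12-month MAE endpoints that use the same component

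*Protocol*

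**What the plan says.** The protocol's endpoint sections, its glossary and the SAP all word the amputation component of MAE the same way: "Unplanned target limb major amputation (above the ankle". The MAE entry in Protocol 15.1 is study-wide and not tied to a visit ("For the purposes of this study, the definition of Major Adverse Event(s) includes").

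MAE at 30 days is the primary safety endpoint (Protocol 5.1; SAP 4.1). MAE is also a secondary endpoint "at 6 and 12 months (as a composite and individual components" (Protocol 2.0 and 5.1; SAP 4.3). Neither document gives the later endpoints their own amputation definition.

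Protocol 15.1 has two relevant amputation entries. The entry for severity has no time limit: "Amputation (major): Any requirement for amputation above the ankle". The entry for 'unplanned' does: "An amputation associated with the target limb that occurs between the index procedure and 30 days that was not previously planned".

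The SAP does not redefine the term. SAP 10.3 sends the reader back: "The Clinical Protocols provide a current Glossary of Terms and Abbreviations".

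**The concern.** The late MAE endpoints depend on the word 'unplanned', and its only definition ends at day 30. Anyone applying the glossary as written would classify a major amputation on day 31 or later as outside the term, and so outside MAE. The 12-month amputation component would then equal the 30-day component by construction.

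The limit also removes the events that this component is there to follow. Exclusion 14 bars subjects with "Planned major amputation of target limb", so a major amputation during follow-up will nearly always be unplanned in the ordinary sense. Rutherford categories 4 and 5 are eligible, so limb loss is a relevant late outcome. At stake is whether the 6- and 12-month MAE rates show the limb loss that occurred.

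**Working it through.** **1. The plan's own figures.** The only stated figures that involve MAE concern the 30-day endpoint. Inputs (SAP 6.1 to 6.3): N = 90, expected MAE 2.0%, goal 11.2%, expected technical success 97%, goal 85%, one-sided exact binomial tests at 0.025.

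- Safety: P(X ≤ 4 | 90, 0.112) = 0.0218 and P(X ≤ 5 | 90, 0.112) = 0.0537, so the rule is at most 4 MAEs. Power = P(X ≤ 4 | 90, 0.02) = 0.9652 (stated 96.5%).
- Effectiveness: at least 84 of 90, exact alpha 0.0131, power 0.9812 (stated 98.1%).
- Joint: 0.9652 × 0.9812 = 0.9471 (stated 94.7%).

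All three reproduce. None changes if the 30-day limit is removed, because the primary endpoint stops at 30 days anyway.

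**2. The definition traced through each time point.**

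| Endpoint | Amputation component | Effect of the 30-day window |
|---|---|---|
| MAE at 30 days (primary) | unplanned, major, target limb | none; the window coincides |
| MAE at 6 months (secondary) | same wording | no event after day 30 qualifies |
| MAE at 12 months (secondary) | same wording | no event after day 30 qualifies |

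On the nominal 360-day schedule, (360 − 30)/360 = 330/360 = 92% of follow-up time is closed to the component. This is a share of time, not of amputations.

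**3. Who is affected in the composite.** MAE is counted per subject (Protocol 9.2.1). A subject with a late amputation still enters the 6- or 12-month composite through CD-TLR or cardiovascular death. The composite is understated only for late amputees with no other counted component, so by at most the amount by which the component is understated. Primary patency does not fill the gap, because its definition has no amputation term.

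**4. Size.** The documents give no late amputation rate. Assume that a proportion r of subjects have a first unplanned target-limb major amputation between day 31 and month 12. Expected omissions = n × r. The chance of at least one = 1 − (1 − r)^n.

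For the primary analysis cohort, the limit reaches all 90 subjects if Mini S has the same glossary entry. If only FORWARD has it, the limit reaches at least 50% × 90 = 45 subjects.

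| r (assumed) | n = 90: expected; P(≥1) | n = 45: expected; P(≥1) |
|---|---|---|
| 1% | 0.9; 60% | 0.45; 36% |
| 5% | 4.5; 99% | 2.25; 90% |

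At r = 2% and n = 90 the figures are 1.8 and 84%. In the full cohort of up to 125 (SAP 1), 1-5% gives 1.25-6.25 omissions. If the limit applies only to FORWARD's maximum of 75 subjects, it gives 0.75-3.75.

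**The case against.** The other side has four good arguments.

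- **Late amputations are not lost.** A reader might infer that follow-up after day 30 yields nothing on amputation. The documents do not support that. Adverse events are collected through 12 months (Protocol 10.4.1), and the CEC adjudicates amputations (Protocol 13.1). SAP Appendix A lists target limb amputations, without the word 'unplanned' and alongside MAE, among the clinical endpoints with a rate for each reporting period. What is at risk is whether the event counts as an MAE. Appendix A does not define 'unplanned', however, so it does not repair the MAE rates.
- **The CEC may already have a wider rule.** Protocol 13.1 lets it develop its own criteria, and its charter is not among the documents. So it cannot be said that no late amputation will ever count as an MAE, nor that the reported rates will be falsely favourable. It can be said that neither the protocol nor the SAP states a wider rule.
- **The primary result is untouched.** This stands in full. No hypothesis, performance goal or power is attached to MAE at 6 or 12 months.
- **The size is assumed.** This also stands. The 1-5% range has no source in the documents, the cohort includes Rutherford 2 and 3 claudicants, and the Mini S glossary is not available. The table in the working therefore shows both cohort sizes.

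A reader might also take the limit for a deliberate choice to drop late events. Its match with the primary endpoint makes wording drafted for 30 days and not carried forward the more natural explanation, though the documents do not settle this.

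**Conclusion.** The contradiction is real and follows from the text alone: a definition that ends at day 30 is used by endpoints at 6 and 12 months. Read literally, and unless the CEC charter provides otherwise, the amputation component of those endpoints can gain no event after day 30. The composites are then understated for subjects whose only MAE would have been a late amputation.

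Under the assumed 1-5% late rate, about 0.9-4.5 amputations in 90 subjects would be left out of MAE if both studies share the definition, or about 0.45-2.25 if it reaches only 45 US subjects. Where the definition applies, the 12-month component is understated by the assumed rate (1-5 percentage points), and the composite by up to that amount.

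Severity is moderate: secondary, descriptive safety endpoints only.

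**What to change.** In Protocol 15.1, remove the phrase that confines unplanned amputation to the interval from the index procedure to 30 days. Let the 30-day, 6-month and 12-month analyses each apply their own cut-off, as SAP Appendix A already does for clinical endpoints.

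When editing, keep the requirement that the event follows the index procedure, and make clear that 'planned' means planned before that procedure. Otherwise an amputation scheduled during follow-up could be argued to be planned. State the same wording in the SAP and the CEC charter, and align Mini S with it.

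The cost is one definition and the matching charter text. No new data are needed, and the sample size, power and primary analysis stay as they are. The downside is that the 6- and 12-month MAE rates may be slightly less favourable.

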15.2 List of Abbreviations

ABI	Ankle-Brachial Index
ACC	American College of Cardiology
ACS	Acute Coronary Syndrome
ADE	Adverse Device Effect
AE	Adverse Event
AHA	American Heart Association
BTK	Below-the-Knee
CEC	Clinical Events Committee
CFR	Code of Federal Regulations
CIP	Clinical Investigation Plan
CKD-EPI	Chronic Kidney Disease Epidemiology Collaboration
CLI	Critical Limb Ischemia
CRF	Case Report Form
CRO	Contract Research Organization
CTA	Computed Tomography Angiogram
CTO	Chronic Total Occlusion
DCB	Drug-Coated Balloon
DES	Drug-Eluting Stent
DSM	Data and Safety Monitor
DUS	Duplex Ultrasound
eCRF	Electronic Case Report Form
EDC	Electronic Data Capture
ESC	European Society of Cardiology
ESVS	European Society of Vascular Surgery
GCP	Good Clinical Practice
GFR	Glomerular Filtration Rate
IB	Investigator Brochure
ICF	Informed Consent Form
ICH	International Council for Harmonisation
IFU	Instruction for Use
IRB	Institutional Review Board
ISO	International Organization for Standardization
ITT	Intent-to-Treat

No.: CP 67398

REV. C

TITLE: FORWARD PAD IDE Study Protocol

CLASS: CLINICAL PROTOCOL

PAGE 60 OF 65

IVL	Intravascular Lithotripsy
IVUS	Intravascular Ultrasound
MAE	Major Adverse Event
MALE	Major Adverse Limb Event
MDR	Medical Device Reporting
MRA	Magnetic Resonance Angiography
OCT	Optical Coherence Tomography
OTW	Over-the-Wire
PAD	Peripheral Artery Disease
PARC	Peripheral Academic Research Consortium
POD	Post-Operative Death
PTA	Percutaneous Transluminal Angioplasty
RC	Rutherford Category
RVD	Reference Vessel Diameter
SADE	Serious Adverse Device Effect
SAE	Serious Adverse Event
TBI	Toe-Brachial Index
TLR	Target Lesion Revascularization
TVR	Target Vessel Revascularization
USADE	Unanticipated Serious Adverse Device Effect

 SHOCKWAVE <small>MEDICAL INC</small>	No.: CP 67398	REV. C
	TITLE: FORWARD PAD IDE Study Protocol	
	CLASS: CLINICAL PROTOCOL	PAGE 61 OF 65

17.0 SUBJECT INFORMED CONSENT

The subject informed consent template will be provided as a separate attachment.

 SHOCKWAVE MEDICAL INC	No.: CP 67398	REV. C
	TITLE: FORWARD PAD IDE Study Protocol	
	CLASS: CLINICAL PROTOCOL	PAGE 64 OF 65

18.0 CASE REPORT FORMS

Draft case report forms will be provided as a separate attachment.

 SHOCKWAVE <small>MEDICAL INC</small>	No.: CP 67398	REV. C
	TITLE: FORWARD PAD IDE Study Protocol	
	CLASS: CLINICAL PROTOCOL	PAGE 65 OF 65

19.0 REVISION HISTORY

Revision	Release Date	DCO #	Reason(s) for Revision	Doc Owner
A	2/22/2023	24706	Initial release.	Clinical
B	3/17/2023	25493	
 • Updated Indication for use in section 2.0 and 4.2 • Removed EDC vendor name from section 12.9 • Updated study duration in section 2.0 • Removed figure 2 (duplicate) 	Clinical
C	5/12/2023	25955	
 • Updated nomenclature pertaining to IVL catheter and catheter configurations under study • Administrative changes 	Clinical

1. INTRODUCTION

This statistical analysis plan (SAP) outlines the data and procedures used for assessing the safety and effectiveness of the Shockwave Medical JAVELIN Peripheral IVL Catheter over pooled data from two studies: the Mini S Australia and New Zealand Study (CP65324) and the FORWARD IDE Study (CP67398).

Data from subjects enrolled under the IDE protocol will be pooled with data from the Mini S Australia and New Zealand Study to form a pooled primary analysis cohort of 90 subjects. Results of the first 90 consecutively enrolled subjects with evaluable data across both studies (with a minimum of 50% of patients from the US) will comprise the primary analysis cohort and will be submitted to FDA to support a Premarket Notification 510(k) application for the JAVELIN IVL Catheter. Results of the full cohort from both studies in up to 125 subjects will be provided to FDA in annual progress reports.

2. STUDY OBJECTIVE

The objective of this Clinical Proposal is to use the data that Shockwave Medical is currently collecting from the two clinical studies described above to demonstrate the safety and effectiveness of the Shockwave Medical JAVELIN Peripheral IVL Catheter compared to pre-defined performance goals. This document may modify and supersede the statistical plans outlined in the respective study protocols.

3. STUDY DESIGN

The ongoing Mini S Australia and New Zealand Study is a prospective, multi-center, single-arm study. The FORWARD IDE Study is also a prospective, multi-center, single-arm study. Results of the first 90 consecutively enrolled analyzable subjects across both studies (with a minimum of 50% of patients from the US) will comprise the pooled primary analysis cohort and will be submitted to support a Premarket Notification 510(k) submission for the Mini S IVL Catheter.

4. STUDY ENDPOINTS

The primary and secondary endpoints for the pooled cohort are presented below. To reduce bias and ensure poolability of data, all endpoints for both studies will be adjudicated by the same independent Clinical Events Committee as well as the same angiographic and ultrasound core labs.

4.1. Primary Safety Endpoint

The primary safety endpoint for the pooled cohort is Major Adverse Events (MAE) at 30 days defined as a composite of:

- Cardiovascular death
- Unplanned target limb major amputation (above the ankle)
- Clinically-driven target lesion revascularization (CD-TLR)

4.2. Primary Effectiveness Endpoint

The primary effectiveness endpoint is **Technical Success** defined as final residual stenosis $\leq 50\%$ without flow-limiting dissection (\geq Grade D) of the target lesion by angiographic core lab.

4.3. Secondary Endpoints

- **Serious angiographic complications** defined as flow-limiting dissection (\geq grade D), perforation, distal embolization, or acute vessel closure as assessed by the angiographic core lab.
- **IVL Technical Success (post-dil)** defined as *post-dilatation* residual stenosis $\leq 50\%$ without flow-limiting dissection (\geq Grade D) of the target lesion by angiographic core lab (measured immediately following mandatory post-dilatation).
- **IVL Device Success** defined as the ability to deliver, advance across the target lesion, pressurize, pulse, flush and retrieve the JAVELIN IVL Catheter.
- **Technical Success (final)** defined as *final* residual stenosis $\leq 30\%$ without flow-limiting dissection (\geq Grade D) of the target lesion by angiographic core lab.
- **MAE** at 6 and 12 months (as a composite and individual components)
- **Primary Patency** at 12 months defined as:
 - Above the knee lesions: freedom from $\geq 50\%$ restenosis as determined by Duplex Ultrasound (DUS) and freedom from Clinically-Driven Target Lesion Revascularization (CD-TLR)
 - Below the knee lesions: freedom from both total occlusion (100% diameter stenosis by DUS) in all of the target lesions in a flow pathway, as well as a CD-Revascularization (CD-TLR).

